#### *1.5 CONFLICTS OF INTEREST STATEMENT*

The investigators have no conflicts of interest to declare for this study.

## 2. STUDY SUMMARY

[figure not shown]
Trial Title	Remote monitoring of disease and physical activity in rheumatoid arthritis: a pilot study
Summary of Study Design	Observational longitudinal cohort study
Summary of Participant Population	Participants with established rheumatoid arthritis with active disease commencing a new disease-modifying anti-rheumatic drug
Planned Sample Size	20 participants
Planned Number of Sites	1
Follow Up Duration	3 months
Planned Study Period	11 months
Primary Objectives	To demonstrate the feasibility of remote disease activity monitoring in participants with rheumatoid arthritis, to support a future clinical efficacy trial.
Primary endpoint:	Correlation and agreement of remote methods of disease activity measurement (patient reported outcome measures, and activity/gait/cardiorespiratory monitors) compared to face-to-face assessments of disease activity in 28 joints with C-reactive protein (DAS28-CRP) scores.
Study Intervention:	Nil (standard clinical care, observational only)

## 3. BACKGROUND INFORMATION

Rheumatoid arthritis (RA) is a common disease affecting 1 in 100 adults in the United Kingdom,[1] and is characterised by joint pain and swelling, and general features such as fatigue.[2] Patients with RA are prescribed disease modifying anti-rheumatic drugs (DMARDs) in order to prevent joint damage and improve symptoms.[3] In current clinical practice, the response to DMARD therapy is assessed by a clinician who assesses the number of tender and swollen joints, together with a laboratory marker of inflammation, to calculate a disease activity score in 28 joints (DAS28) (Appendix A). The need for face-to-face hospital clinic reviews makes such disease activity monitoring a time-consuming and expensive process, further compounded by reduced outpatient clinic capacity as a result of the COVID-19 pandemic. Furthermore, DAS28 monitoring has been criticised for under-representation of subjective symptoms such as fatigue, and potential insensitivity to impact on physical function.

In contrast to traditional DAS28 monitoring, various patient reported outcome measures (PROMs) have been developed which utilise self-completed patient questionnaires to quantify a range of disease activity parameters including fatigue, pain, mood and physical function.[4] Such PROMs can be completed remotely without the need for hospital visits, and can quantify subjective parameters not explicitly captured by DAS28. Furthermore, recent technological advances in sensor technology now form the basis of a range of wearable devices, which can remotely record and quantify physical activity, gait characteristics, and physiological parameters such as heart rate.[5] PROMs have been shown to correlate closely with DAS28,[4] and activity tracker data has been shown to correlate with arthritis flares,[5] but the clinical efficacy of both approaches in remote RA disease activity monitoring is yet to be confirmed.

In this pilot study (**Figure**), we propose to recruit 20 participants with RA with active disease who are newly starting a DMARD. Participants will be followed for 3 months, with monthly face-to-face visits to measure DAS28 score. Throughout the study, participants will complete weekly PROM measurements in the form of the simple 5-question RA Disease Activity Index 5 (RADAI-5, Appendix D), captured electronically using the British Society for Rheumatology ePROMs online portal,[6] with weekly email reminders to support participant uptake. In addition, at each monthly visit participants will be provided with activity trackers (lower back and wrist – Axivity AX6) and a combined activity and cardiorespiratory monitor (VitalPatch) to be worn for 7 days. Additional PROMs including FACIT-F[7] and MFS[8] (fatigue), HAQ-DI[9] (physical function), PHQ-2[10] (anxiety/depression) and EQ-5D-5L[11] (general health) will be captured at the monthly visits, in order to collect information necessary for interpretation of the activity monitor data. Importantly, participant acceptability will be assessed through questionnaires, and by invitation of participants to an optional participant focus group to identify areas of potential improvement. Ultimately the findings of this pilot study will support further funding applications both for a definitive randomised clinical trial to demonstrate the clinical efficacy of remote monitoring in RA management, and for further research to refine and validate potential digital biomarkers of disease activity.

**Figure** – Study design. Participants will be reviewed at monthly intervals for DAS28 assessment, completion of additional PROMs, and provision of activity and heart rate monitors to be worn for 7 days and then returned by post.

## 4. STUDY DESIGN

### 4.1 Aims

1. To demonstrate the feasibility of remote RA disease activity monitoring, to support a future clinical efficacy trial
2. To identify digital biomarkers of disease activity based on wearable monitoring devices, for future development and validation

### 4.2 Primary objectives

1. To assess the correlation and agreement between paired DAS28 and RADAI-5 measurements
2. To assess the longitudinal responsiveness and minimal detectable change in repeated RADAI-5 measurements
3. To assess the acceptability of remote PROM capture and activity/gait/heart rate monitoring, through the use of participant questionnaires and focus groups

### 4.3 Secondary objective

1. To use validated algorithms and novel machine-learning methods to identify activity, gait and heart rate monitor signatures that correlate with, and are predictive of, DAS28- and RADAI-5-defined disease activity

### 4.4 Study type

This will be a prospective observational cohort study conducted at a single study site.

## 5. RECRUITMENT OF PARTICIPANTS

### 5.1 Inclusion criteria

1. Diagnosis of rheumatoid arthritis according to the 1987 American College of Rheumatology (ACR) (Appendix B) or 2010 ACR/European Alliance of Associations for Rheumatology (EULAR) classification criteria (Appendix C) applied at any time since diagnosis.
2. Participant about to commence (i.e. planned within next 4 weeks), or recently commenced (i.e. within past 8 weeks), a new disease-modifying anti-rheumatic drug (i.e. conventional synthetic DMARD, Janus-kinase inhibitor or biologic therapy)
3. Able to walk at least four metres independently without walking aids
4. Participant willing to commit to complete remote monitoring measurements and wear monitoring devices

### 5.2 Exclusion criteria

1. Unable to read or communicate in English
2. Current participation within an interventional clinical trial (participation in another observational trial is permitted)

3. Inability to provide informed consent
4. Age less than 18 years
5. Current diagnosis of a movement disorder
6. Current pregnancy

### *5.3 Recruitment strategy*

Potentially eligible patients attending rheumatology outpatient appointments will be identified by the doctor or nurse specialist that they see in clinic. If a research nurse is available, then they will provide the participant information leaflet and discuss the study with the patient. If the patient is interested in joining the study, then either the research nurse or the patient can book the initial study appointment. Alternatively, and with the patient's verbal consent as documented in the clinical records, the referring healthcare professional may provide contact details (name, address and telephone number) of the patient by secure NHS.net email to a study researcher, who will contact the patient by telephone to discuss the study further. If the patient would like to join the study, a participant information sheet will be posted to the patient. Potentially eligible patients who are retrospectively identified by their clinical team (by review of electronic clinical records and/or clinical databases) may also be recruited to the study.

Within the Newcastle Hospitals rheumatology department, “Change of Medication” forms are completed by clinicians when patients change their arthritis drug treatment. In addition to the recruitment strategy above, these Change of Medication forms will be reviewed by the Chief Investigator (or other clinician working within the department who is appropriately delegated on the study delegation log) to identify patients with rheumatoid arthritis who have (or will shortly) start a new arthritis drug, and thus be potentially eligible to enrol in the study. Identified patients will then be sent a letter to invite them to contact the research team to discuss the study and participate if they so wish.

### *5.4 Target recruitment size*

This is a pilot study, designed to support a future definite clinical efficacy trial. As such this pilot study is not statistically powered, but rather is intended to provide preliminary data to estimate the feasibility and acceptability of remote monitoring in patients with RA, and generate an exploratory dataset for derivation of putative digital biomarkers of arthritis activity. A target of 20 participants will be recruited to the study, based upon the limited available resources for purchasing monitoring equipment in this small pilot study.

### *5.5 Closure of study*

Recruitment to the study will close upon recruitment of the 20th participant or on 30/06/23, whichever is earlier. The study will close on 30/09/23.

## **6. STUDY VISITS**

### 6.1 Initial study visit

Participants attending their initial appointment will undergo the following procedures.

1. All participants will have the opportunity to discuss the study further with a study investigator before signing the consent form.
2. Participant eligibility for study enrolment based on the inclusion and exclusion criteria will be confirmed.
3. Participants will be asked to provide baseline information including age, sex, address, telephone number, email address, past medical history, Clinical Frailty Score,[12] Charlson Comorbidity Index,[13] current medications, smoking status and alcohol intake.
4. The participant's height and weight will be recorded.
5. A researcher will then examine the participant to ascertain the 28-joint tender and swollen counts, a patient visual analogue scale, and a physician visual analogue scale, required to assess disease activity using the DAS28-CRP score (Appendix A).
6. The participant will then complete a RADAI-5 questionnaire (Appendix D).
7. The participant will then be asked to complete the following paper questionnaires:
  - a. Health Assessment Questionnaire Disability Index (HAQ-DI)
  - b. FACIT-F and MFS
  - c. PHQ-2
  - d. EQ-5D-5L
8. Participants will then be shown how to access the ePROMs portal. Written information will be provided to participants to explain this further.
9. Participants will then be instructed on how to wear and activate the remote monitoring digital tracker devices. Written information will be provided to explain this further. The following devices will be provided, and should be worn simultaneously for 7 days following the study visit:
  - a. Axivity AX6 monitor and adhesive dressing – for application to lower back
  - b. Axivity AX6 monitor and wrist strap – for application to wrist
  - c. VitalPatch self-adhesive monitor – for application to left upper chest wall
  - d. A study mobile phone and charger – for data linkage and downloading from the VitalPatch device
10. Blood tests will be taken as per below, thus avoiding additional hospital attendances for mandatory routine clinical blood monitoring during the study period. These results will be passed on to the local clinical DMARD monitoring service, and any necessary action taken by the local clinical team. In the event that a participant has blood monitoring more frequently than once every 4 weeks, then any blood tests required before the date of the next study visit will be performed by the clinical DMARD monitoring service as per usual routine practice.
  - a. Full Blood Count (FBC)
  - b. Erythrocyte sedimentation rate (ESR)
  - c. C reactive protein (CRP)
  - d. Urea and electrolytes (U&Es)
  - e. Liver function tests (LFTs)
11. Participants will be provided with the following documents at the end of the visit:

- a. Blank paper questionnaires, for completion within the 48 hours prior to their next study visit
  - i. Health Assessment Questionnaire Disability Index (HAQ-DI)
  - ii. FACIT-F and MFS
  - iii. PHQ-2
  - iv. EQ-5D-5L
- b. A pre-paid addressed envelope, to post back the reusable Axivity AX6 devices to the researcher team after 7 days

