### 6.3 Week 12 visit

1. Participants will be asked to verbally confirm their willingness to continue in the study.
2. Any change in concurrent medications will be recorded.
3. Any adverse events occurring since the last clinic visit will be recorded.
4. A researcher will then examine the participant to ascertain the 28-joint tender and swollen counts, a patient visual analogue scale, and a physician visual analogue scale, required to assess disease activity using the DAS28-CRP score (Appendix A).
5. The participant will then complete a RADAI-5 questionnaire.
6. Remote self-entered RADAI-5 data will be reviewed on the ePROMs platform (see 6.4 below)
7. The pre-filled questionnaires provided to the participant at their last visit will be collected. If the participant has not had the opportunity to complete these or has not brought them to the appointment, then they will be asked to complete the questionnaires during the study visit:
  - a. Health Assessment Questionnaire Disability Index (HAQ-DI)
  - b. FACIT-F and MFS
  - c. PHQ-2
  - d. EQ-5D-5L
8. Participants will then be reminded on how to wear and activate the remote monitoring digital tracker devices, and how to access the ePROMs portal.
9. Participants will be provided with the following devices, to wear simultaneously for 7 days following the study visit:
  - a. Axivity AX6 monitor and adhesive dressing – for application to lower back
  - b. Axivity AX6 monitor and wrist strap – for application to wrist
10. Blood tests will be taken as per below, thus avoiding additional hospital attendances for mandatory routine clinical blood monitoring during the study period. These results will be passed on to the local clinical DMARD monitoring service, and any necessary action taken by the local clinical team. In the event that a participant has blood monitoring more frequently than once every 4 weeks, then any blood tests required before the date of the next study visit will be performed by the clinical DMARD monitoring service as per usual routine practice.
  - a. Full Blood Count (FBC)
  - b. Erythrocyte sedimentation rate (ESR)
  - c. C reactive protein (CRP)

- d. Urea and electrolytes (U&Es)
- e. Liver function tests (LFTs)

11. The study smartphone and charger will be collected from the participant.

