#### *6.8 End of study*

If the participant declines to take part in the optional focus group (section 6.5), then the week 12 visit will be their final study visit. The participant will exit the study 7 days after this visit (i.e. at the end of their final remote monitoring device measurement period).

If the participant agrees to take part in the optional focus group (section 6.5), then a further optional focus group visit will occur no later than 180 days from the date of their week 12 visit. No additional study visits are permitted between the week 12 and optional focus group visits. No blood monitoring or disease activity measurements (remote or otherwise) will be performed as part of the research study beyond 7 days after the week 12 visit. The participant will exit the study at the end of the optional focus group visit.

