### **9. ETHICAL CONSIDERATIONS**

Participants will be required to attend for face-to-face hospital visits on four occasions during study follow-up. To avoid additional study visits beyond standard clinical care, we have incorporated DMARD blood safety tests within the study visit schedule. This will avoid additional trips to hospital, with potential for increased COVID-19 infection risk.

The use of an online ePROMs portal requires a computer or mobile device, internet access, and a modest degree of digital literacy to access the webpage interface. We recognise that these requirements may have an indirect effect of excluding participants of certain socioeconomic backgrounds from participating in the project. However, alternative methods of data capture (such as paper forms) are not feasible owing to the frequency of ePROMs assessments and the need to link these in real time to DAS28 and activity tracker data. Furthermore, a specific aim of this pilot project is to assess the acceptability and feasibility of internet-based ePROMs capture, to guide decisions on use in future larger studies. The screening log for this study will record where participants were unable to participate due to technological barriers, to ascertain if this is likely to be a significant barrier to recruitment to future studies and thus guide the need for future mitigation strategies.

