## 15. SCHEDULE OF EVENTS

Activity	Visit 1: day 0	Visit 2: Day 28 (+/- 7 days)	Visit 3: Day 56 (+/- 7 days)	Visit 4: Day 84 (+/- 7 days)	Optional Focus Group (<180 days)
Informed consent	X				
Study eligibility assessment	X				
Medical history	X				
Clinical frailty score	X				
Charlson Comorbidity Index	X				
Height and weight	X				
Concomitant medications	X	X	X	X	
Adverse event recording and reporting		X	X	X	
Joint counts / VAS scores	X	X	X	X	
RADAI-5	X	X	X	X	
HAQ-DI	X	X	X	X	
FACIT-F	X	X	X	X	
MFS	X	X	X	X	
PHQ-2	X	X	X	X	
EQ-5D-5L	X	X	X	X	
Register on ePROMs portal	X				
Instruction on use of remote monitoring devices	X				
Provision of study smartphone and charger	X				
Review of ePROMs record		X	X	X	
Provision of monitoring devices and pre-paid envelope	X	X	X	X	
Collection of study smartphone and charger					X
Bloods (CRP, ESR, FBC, U&Es, LFTs)	X	X	X	X	
Provision of paper questionnaires for next visit	X	X	X		
Experience feedback questionnaire				X	
Optional focus group					X

CRP: C-reactive protein, ESR: erythrocyte sedimentation rate, EQ-5D-5L: EuroQol 5D-5L, FACIT-F: Functional Assessment of Chronic Illness Therapy – Fatigue, FBC: full blood count, HAQ-DI: Health Assessment Questionnaire Disability Index, LFTs: liver function tests, MFS: Mental Fatigue Scale, PHQ-2: Patient Health Questionnaire 2, RADAI-5: Rheumatoid Arthritis Disease Activity Index 5, U&Es: urea and electrolytes.

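### The back-up clause for DMARD safety bloods assumes visits at most 28 days apart, but the visit windows allow gaps of up to 42 days

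*Protocol*

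**What the plan says.** Protocol Section 6.1, item 10, lists the bloods taken at the visit and gives the reason: "thus avoiding additional hospital attendances for mandatory routine clinical blood monitoring during the study period". Items 10 of Sections 6.2 and 6.3 repeat this, and Section 9 makes the same point to the ethics reader: "we have incorporated DMARD blood safety tests within the study visit schedule".

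Each item 10 then adds a back-up arrangement with a condition attached: "In the event that a participant has blood monitoring more frequently than once every 4 weeks, then any blood tests required before the date of". Such between-visit tests are left to the clinical DMARD monitoring service. Results of study bloods go to that service, and the local clinical team takes any action needed.

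The schedule in Section 15 puts visit 1 at day 0 and gives the other three visits a window of 7 days either side of days 28, 56 and 84. The column for the second visit, for example, is headed "Visit 2: Day 28 (+/- 7 days".

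The week 12 text in Section 6.3 keeps the forward reference: "any blood tests required before the date of the next study visit will be performed by the clinical DMARD monitoring service as per usual routine". Section 6.8 says of the period after that visit: "No blood monitoring or disease activity measurements (remote or otherwise) will be performed as part of the research study beyond 7 days after the week" (meaning the week 12 visit).

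**The concern.** The condition in item 10 splits participants into two groups. Those monitored more often than 4-weekly have their interim tests assigned to the clinical service. For everyone else the text is silent, which makes sense only if the next study visit always arrives within 4 weeks of the last. The windows in Section 15 do not guarantee that. A participant on exactly 4-weekly monitoring falls outside the condition, yet can have a test fall due before the next visit with every visit in window and no protocol deviation.

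These are safety tests in people who are about to start, or have recently started, a DMARD. The protocol offers the combined blood draw as a convenience to them. It should not leave unclear who takes a test that falls between visits. No endpoint or analysis is affected.

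**Working it through.** The protocol states no between-visit gap, so there is no figure of its own to reproduce. The check is interval arithmetic on Section 15.

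**Inputs (Section 15), with windows counted from day 0 as the column headings read**
- Visit 1: day 0, no window.
- Visit 2: 28 ± 7, so days 21 to 35.
- Visit 3: 56 ± 7, so days 49 to 63.
- Visit 4: 84 ± 7, so days 77 to 91.
- Condition in item 10: monitoring interval strictly shorter than 4 weeks, that is, under 28 days.

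**Formula.** Longest gap = latest day of the later visit minus earliest day of the earlier visit. Shortest gap = earliest day of the later visit minus latest day of the earlier visit. Possible lateness for a 28-day interval = longest gap − 28.

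| Interval | Shortest gap | Longest gap | Beyond 28 days |
|---|---|---|---|
| Visits 1 to 2 | 21 − 0 = 21 | 35 − 0 = 35 | 7 |
| Visits 2 to 3 | 49 − 35 = 14 | 63 − 21 = 42 | 14 |
| Visits 3 to 4 | 77 − 63 = 14 | 91 − 49 = 42 | 14 |

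On the nominal days every gap is exactly 28 and the clause works. It fails once a visit moves later relative to the one before.

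**Can one participant have two 42-day gaps?** No. The first needs visit 3 on day 63 and the second needs it on day 49. Visits 2 and 4 are at most 91 − 21 = 70 days apart, so if both later gaps are long, the shorter of the two is at most 70 / 2 = 35 days (visits on days 21, 56 and 91).

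**Dependence on the required interval.** The protocol gives no participant's interval, so this is a range under assumed values:
- 28 days: up to 7 days late in the first interval and up to 14 in a later one.
- 35 days: none late in the first interval (35 − 35 = 0), up to 42 − 35 = 7 days in a later one.
- 42 days or more: none late.

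**If windows ran from the previous visit instead.** Every gap would then be at most 28 + 7 = 35 days. The mismatch would be smaller but would remain.

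**Week 12.** Section 6.3 item 10 refers to the next study visit. Under Section 6.8 the only later visit is the optional focus group, up to 180 days on, and the Section 15 row for bloods has no entry in that column. The phrase therefore points to a visit that takes no blood and may not happen.

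**The case against.** The strongest reply is that this is an observational study under standard clinical care (Section 2). Study results go to the clinical DMARD monitoring service, and no sentence suspends that service's own monitoring. Section 9 speaks of sparing people extra trips, not of moving responsibility. This stands. A reader might infer that overdue tests have nobody assigned to take them; the documents do not support that. The protocol is silent for one group, and silence is not a withdrawal of care. What remains is that the text chose to say when the clinical service acts between visits, and said so for one group only.

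A reader might also try to count those affected. If visits fell evenly over the days of their windows, 7/15 (46.7%) of intervals would exceed 28 days, or 60 × 7/15 = 28 of the 60 intervals in 20 participants. That counts visit intervals, including overruns of one day, and not overdue tests. A test is overdue only if the participant's required interval is shorter than the gap, and the number affected could be zero.

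The 42-day gap also needs a visit 7 days early followed by one 7 days late. Against the fixed calendar of days 28, 56 and 84, no in-window visit is more than 7 days late; the 14 days is measured from the previous test. This qualifies the size but does not remove the mismatch.

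Finally, withdrawal (Section 6.6) and discharge for pregnancy (Section 7.6) might look like further gaps. They are not. Withdrawal returns the person to ordinary care, and Section 7.6 already requires the referring rheumatologist and GP to be informed.

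**Conclusion.** The point holds as a mismatch between item 10 of Sections 6.1 to 6.3 and the windows in Section 15. The condition in item 10 presumes gaps of at most 28 days. The schedule permits 35 days in the first interval and 42 days in either later one, but not 42 in both. For a participant monitored every 4 weeks, the clause does not say who takes a test that falls due before a late in-window visit, and that test could be up to 14 days past due.

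This assumes that windows are counted from day 0, that the 4-week condition is read literally, and that lateness is measured from the last test. It does not establish that any test will be missed, or how many participants could be affected.

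The forward reference at week 12 is a genuine but minor slip. Section 6.8 expressly ends study bloods, so the gap between visits does not arise there. The change is worth making because the tests concern safety and the amendment is cheap.

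**What to change.** Reconcile item 10 in Sections 6.1, 6.2 and 6.3 with the windows in Section 15. The existing clause should depend on whether a test falls due before the actual date of the next study visit, and not on the 4-week frequency condition. The required monitoring interval stays with the clinical service; this review takes no view on it.

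Separately, reconcile the forward reference in Section 6.3 item 10 with Section 6.8, since no further study bloods follow that visit.

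The cost is a wording amendment to one paragraph that appears three times. A few participants may need a routine blood test outside a study visit, which slightly reduces the convenience described in Section 9. Visit timing, endpoints and analysis do not change.
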